5.0 STATISTICAL CONSIDERATIONS

- Primary and Secondary Endpoints
To determine if the use of a metronome increases intensity of exercise performance as measured by an increase in the BORG scale.
To determine if the use of a metronome improves self-reported and objective measures of functional outcome performance by using the GROC and the 30 second sit to stand and noting an improvement in scores.
- Measures to Avoid Bias

Study participants will be randomized as previously noted.

Statistical Methods, Sample Size and Power

A minimum of 102 participants will be needed for a medium effect, a power of 0.8 and a level of significance of 0.05. The data analysis plan will be an Analysis of Covariance (ANCOVA), with the baseline data as the covariate.

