1.0 BACKGROUND INFORMATION AND RATIONALE

○ Introduction

Physical therapy patients experiencing musculoskeletal pain often lack effort and consistency when performing aquatic exercises. Studies have shown that the use of acoustic stimuli, such as music and the beeps of a metronome, improve performance and efficiency in runners. However, it has not been determined if the use of a metronome can improve the outcomes of patients participating in aquatic physical therapy.

○ Relevant Literature and Data

In 2012, one of two adults in the United States were diagnosed with musculoskeletal conditions. In the same year, 25.5 million people lost an average of 11.4 days of work due to back and neck pain. (1)

The benefits of aquatic therapy make it well suited for the treatment of musculoskeletal conditions. These benefits include decreased weight bearing, the thermal and compressive effects of water on the body, and less cardiovascular stress during exercise. (2)

In a 2008 study it was demonstrated that the use of acoustic pacing device can improve consistency and performance during and between exercise sessions in an aquatic environment among runners(3) Studies have also shown that an aquatic exercise program can improve strength and function among varied age groups.(4,5) However, what isn't known is if the use of an acoustic pacing device, such as a metronome, can improve the outcomes of patients in an aquatic therapy program.

STUDY OBJECTIVES

○ Primary Objective

To determine if the use of a metronome improves measures of functional outcome in aquatic therapy.

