2.0 INVESTIGATION PLAN

○ General Schema of Study Design

Quasi-experimental

- Study Duration, Enrollment and Number of Sites
 - 2.○ .1 Date Range of Study
(January 3, 2019 - December 1st, 2019)
 - 2.○ .2 Total Number of Study Sites
Aultman Tusc Therapy
 - 2.○ .3 Total Number of Subjects Projected 120
The statistician projected the study would require 102 participants. I will recruit up to 120 to allow for unforeseen issues. The 120 participants will be divided into a control group of approximately 60 and the metronome group of approximately 60.
- Study Population
 - 2.○ .1 Inclusion/Exclusion Criteria
All patients over the age of 18 will be included in the study except for those that have identified themselves as being pregnant on intake, and those that are unable to hear the metronome or unable to hear it when their hearing aide is removed during treatment.

STUDY PROCEDURES

○ Procedures Involved

During their initial evaluations and again at re-evaluation or discharge, patients will be assessed using a 30 second sit to stand. The patient will be asked to rate their progress using the global rating of change scale at re-evaluation or discharge. The patients will be asked to rate their pain using a numerical pain scale. Their reported pain level will be recorded before and after each treatment. The number reported on initial evaluation and at discharge will be used in the study. The above numbers will be recorded in the patient's electronic chart and on the de-identified flow sheet. All patients will be educated on proper performance of aquatic exercises following normal physical therapy procedures. The patients will be randomly placed into two groups: a control group and a group exercising with the pacing of a metronome. (The metronome does not appear in the FDA's product classification database as a medical device.) The patient's will be randomized by placing 20 poker chips in a bag. There will be 10 white pieces with the letter C and 10 red pieces with the letter M. When a patient is chosen for the study a piece of paper will be drawn out of the bag and they will be assigned to a group by the letter chosen. The bag will be refilled and the process repeated until the study groups are filled.

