The two groups will follow exercise protocols based on their diagnosis. Each session will last approximately 30 to 45 minutes. The length of each treatment will be recorded on the flow sheet. The BORG scale (a valid, subjective measure of perceived exertion) will be used as a monitoring device to ensure that a desired level of exercise intensity is reached. The desired level is a score between 12 and 16. The patients will be asked to rate their level of exertion at the end of each session. Intensity of the exercises will be adjusted the next session if the patient's reported level of exertion does not fall within the desired range. The pain rating, noted above, and the BORG number will be recorded for both groups in the chart and flow

sheet as will be the metronome beats per minute for the study group. The beats per minute of the metronome will be adjusted to the patient's pain free exertion level. Patients in both groups will start with 10-20 repetitions of the exercises depending on their physical ability. The repetitions will be progressed as the patient's strength and endurance improve and noted in the chart and the flow sheet.

The patients in the metronome group will have the metronome synchronized as previously noted on their second aquatic therapy treatment. The beats per minute (BPM) will be increased on the metronome during the series of treatments until the patient can no longer maintain proper technique with the exercises. The patient will be cued to keep pace with the beat of the metronome during the duration of the exercise.

- Visit Schedule
Each individual will participate in the study for the duration of their physical therapy plan of care, typically 10 to 12 visits. Enrollment will be on going during the study period in order to recruit the needed number of participants. Estimated completion date will be May 1st, 2019.
- Recruitment Procedures
Participants will be recruited during their initial physical therapy evaluations. The study will be explained to them and the consent forms will be signed during their first aquatic therapy treatment.
- Data Collection and Management
 - 2.○ .1 Data sources
Participant's initial evaluation will be used to determine age, gender and diagnosis.
 - 2.○ .2 Data Elements to be Abstracted
 - *Numerical pain scale rating*
 - *30 second sit to stand*
 - *BORG (perceived rating of exertion)*
 - *Global Rating of Change (GRoC)*

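### No primary endpoint is named: the functional objective maps to two unranked measures, the sample size of 102 and the baseline ANCOVA name no endpoint, and Borg is both an outcome and a steered score

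*Protocol*

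**What the plan says.** The Study Objectives part of the protocol gives a single primary objective: "To determine if the use of a metronome improves measures of functional outcome in aquatic therapy". It names no measure.

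Section 5.0 has one heading for primary and secondary endpoints and two unlabelled statements under it. The first concerns exertion: "To determine if the use of a metronome increases intensity of exercise performance as measured by an increase in the BORG scale". The second asks whether the metronome "improves self-reported and objective measures of functional outcome performance by using the GROC and the 30 second sit to stand".

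The sample size statement is "A minimum of 102 participants will be needed for a medium effect, a power of 0.8 and a level of significance of 0.05". The analysis statement is "The data analysis plan will be an Analysis of Covariance (ANCOVA), with the baseline data as the covariate". Neither names an outcome, and the sidedness of the test is not given.

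The timing of the measures is in section 2.0, Study Procedures:
- Sit to stand: "During their initial evaluations and again at re-evaluation or discharge, patients will be assessed using a 30 second sit to stand".
- GRoC: "The patient will be asked to rate their progress using the global rating of change scale at re-evaluation or discharge".
- Borg: rated at the end of every session. The same section says that the scale "will be used as a monitoring device to ensure that a desired level of exercise intensity is reached". It sets the desired score at 12 to 16 and has exercise intensity changed at the next session when the score lies outside that range. Neither group is exempt.

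**The concern.** A reader can arrive at different primary endpoints from the same document. Going by order in section 5.0, it is Borg. Going by the stated objective, it is GRoC or sit to stand. If the choice is not fixed before the data are seen, the lead result can be picked afterwards, and the stated significance level of 0.05 no longer describes the risk of a false positive claim.

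The power of 0.8 also depends on the choice, because the outcomes differ in whether a baseline value is available to reduce the residual variance.

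Borg raises a separate difficulty. Section 5.0 counts a rise in the score as an effect, while section 2.0 corrects the score towards a common band in both groups. If the metronome pushes exertion above the band, or control patients fall below it, the rule acts to remove the contrast that the endpoint is meant to detect.

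**Working it through.** **1. Which measure fits which statement**

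| Measure | Fits the functional objective | Value at initial evaluation | Fits the stated baseline ANCOVA directly |
|---|---|---|---|
| 30-second sit to stand | yes | yes | yes |
| GRoC | yes | no (re-evaluation or discharge only) | no |
| Borg | no (exercise intensity) | none listed (end of each session) | not as written |

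Only sit to stand satisfies both the objective and the analysis sentence, but the protocol does not say that it is the primary endpoint.

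**2. Reproducing 102**

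Inputs from the protocol: total 102, medium effect, power 0.8, significance level 0.05, two groups of about equal size. Assumption: medium means a difference of 0.5 SD.

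For a two-sample t test with n per arm, the noncentrality is 0.5 × √(n/2) on 2n − 2 degrees of freedom.

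- n = 51: 0.5 × √25.5 = 2.525, with 100 degrees of freedom.
- One-sided 0.05: critical value 1.660, power 0.806. At n = 50 power is 0.799, so 51 per arm is the smallest size that reaches 0.8, and 2 × 51 = 102. This matches the protocol's figure exactly.
- Two-sided 0.05: critical value 1.984, power 0.706. Reaching 0.8 would take 64 per arm, or 128.

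For ANCOVA with baseline correlation r, the noncentrality becomes 0.5 / √(1 − r²) × √(n/2) on 2n − 3 degrees of freedom. The protocol gives no r, so a range is shown for n = 51, two-sided:

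| Assumed r | Power |
|---|---|
| 0.3 | 0.746 |
| 0.45 | 0.799 |
| 0.5 | 0.823 |
| 0.7 | 0.938 |

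So 102 agrees with a one-sided test without covariate, or with a two-sided ANCOVA at r of about 0.45. It is a figure for a standardised effect and does not reveal which endpoint was meant.

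**3. Using the recruitment margin**

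Section 2.0 allows up to 120. If all 120 were analysed (60 per arm), two-sided power would be 0.775 without a covariate, 0.81 at r = 0.3 and 0.88 at r = 0.5.

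**4. What an open choice could cost**

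For illustration, suppose each measure were tested at 0.05 and the tests were independent. The chance of at least one false positive would be 1 − 0.95² = 0.0975 for the two functional measures and 1 − 0.95³ = 0.143 for all three. Positive correlation between the measures would lower these figures.

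**5. The two roles of Borg**

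Section 2.0 treats a score outside 12-16 as something to correct at the next session. Section 5.0 treats a higher score as evidence that the metronome works. Under the first rule, patients with high or low scores are moved back towards the same band whichever group they are in, which works against a raw difference between groups. By how much depends on the spread of scores, the session analysed, the size of each adjustment and the true effect. The protocol gives none of these, so no figure is put on it here.

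**The case against.** The strongest reply is that the protocol is less open than it looks. Its only primary objective is functional, and the second endpoint statement uses the same idea and names GRoC and sit to stand for it. A reader might infer from the missing label that the functional objective has no endpoint at all; the text does not support that. This part of the reply stands: the objective has two endpoints. What is missing is a choice between them and an explicit ranking against Borg, which is listed first.

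A reader might also infer that 102 is too few. That is not shown. The protocol states no sidedness, its wording is directional, a one-sided calculation gives 102 exactly, a two-sided ANCOVA with a moderate correlation gives it too, and recruitment may reach 120. The 0.71 holds only for a two-sided test without a covariate at exactly 102.

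Nor does GRoC's lack of a baseline rule out every ANCOVA. The analysis sentence speaks of baseline data in general, so another initial-evaluation variable could serve as covariate. The protocol would have to say which one, or that GRoC is analysed without one.

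On Borg, a reader might conclude that the rule removes the effect or by itself makes the comparison underpowered. The documents do not support that: a smaller raw difference may come with a smaller spread, so the standardised difference need not fall, and the metronome group also has its own pace progression. Only the conflict of roles can be claimed.

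Finally, section 3.0 says that no data are collected before consent at the first aquatic treatment, which might seem to bar the initial sit-to-stand value. But section 2.0 records that value in the patient's chart and lists it among the items to be abstracted, so abstraction after consent is a ready reading. At most, a clarifying sentence is needed.

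A separate statistical analysis plan could hold much of the detail. It does not excuse the absent label, because the protocol has a section for this purpose and leaves the choice open there.

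**Conclusion.** The point holds and should be fixed before data are analysed. The missing primary endpoint and the two roles of Borg can be read directly from the protocol and need no assumption. The power figures rest on an assumed effect of 0.5 SD and, for the ANCOVA, on assumed correlations. They show that the stated 0.8 may or may not be met, depending on endpoint, sidedness and baseline correlation; they do not show that 102 is wrong. For Borg, the conclusion is limited to interpretation: a small or null difference could reflect the adjustment rule as well as an ineffective metronome, and a positive one would not answer the functional objective.

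**What to change.** In section 5.0:

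- Name one functional measure as the single primary endpoint. The 30-second sit to stand is the natural choice, with its initial-evaluation value as the covariate.
- Make GRoC secondary, and state either its covariate or an analysis without one.
- State the endpoint, the sidedness and any baseline correlation behind 102, and restate the power if these do not give 0.8.
- Report Borg by group as a secondary or process measure, with the caveat that the score was steered, and not as the lead evidence of efficacy. Reconcile its roles in sections 2.0 and 5.0. No change to the adjustment rule is proposed.

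If wanted, add a sentence in section 3.0 saying that the initial-evaluation value is taken from the chart after consent.

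The cost is rewording and one power check; no new measurement is needed. The downside is that Borg can no longer be claimed as the lead result.

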3.0 STUDY ADMINISTRATION

- Data Quality. Data collection in the pool will be limited to two Physical Therapist Assistants. There will be 1- 4 Physical Therapist collecting data during the initial evaluation and re-evaluation depending on which PT is referring the patient for aquatic therapy.

Privacy and Confidentiality

- All laws ensuring privacy and confidentiality governed through HIPPA will continue to be practiced.
- Data with patient identifiers will be de-identified by me.
- All files will be stored in a secured and locked location at Aultman Tusc Therapy.

- Confidentiality
See above
- Regulatory and Ethical Considerations
 - 3.○ .1 Risk Assessment
The participants in the study will face no additional risk than those not in the study. As normal physical therapy procedures will be followed for patients receiving aquatic therapy.
 - 3.○ .2 Potential Benefits of Study Participation
Anticipated benefits of participation in the study will be a decrease in the number of visits needed to improve strength and function.
 - 3.○ .3 Informed Consent/Assent and HIPAA Authorization
Informed consent will be obtained by the primary/secondary investigators during the patient's first aquatic therapy treatment. No data will be collected until that point.
 - 3.○ .3.1 Waiver or Alteration of Consent (requesting a waiver)

N/A
 - 3.○ .3.2 Waiver of HIPAA Authorization
N/A

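### Does the single ANCOVA named in the protocol fail for the Global Rating of Change, which has no baseline score?

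*Protocol*

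**What the plan says.** Under its statistical methods heading, section 5.0 gives one method and does not vary it by endpoint: "The data analysis plan will be an Analysis of Covariance (ANCOVA), with the baseline data as the covariate". The endpoint list in the same section has three measures. Borg exertion comes first. The functional aim is then to be judged "by using the GROC and the 30 second sit to stand and noting an improvement in scores".

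The procedures in section 2.0 set the timing:

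- Sit to stand is measured twice: "During their initial evaluations and again at re-evaluation or discharge, patients will be assessed using a 30 second sit to stand".
- GRoC is measured once: "The patient will be asked to rate their progress using the global rating of change scale at re-evaluation or discharge".
- Pain is recorded around every treatment, and for the analysis "The number reported on initial evaluation and at discharge will be used in the study".
- Borg is rated at the end of each session. The metronome is introduced at the second aquatic treatment.

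Section 3.0 describes each "Physical Therapist collecting data during the initial evaluation and re-evaluation". On consent, which is taken at the first aquatic treatment, it adds: "No data will be collected until that point".

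**The concern.** GRoC asks the patient how much they have changed, so an initial GRoC score would have no meaning and none is collected. If the baseline data in section 5.0 means the earlier value of the same measure, the only named analysis cannot be carried out for GRoC. There would also be no earlier GRoC score from which to note an improvement. GRoC is the only self-reported functional measure among the endpoints, so that half of the functional aim would have no usable analysis.

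Two consequences could follow. If the covariate for GRoC were settled only after results by arm were known, several defensible models would be on offer and the 5% error rate would not be protected. Separately, if no data may be collected before consent, the initial sit to stand and pain values that could serve as covariates appear to be out of bounds, because the initial evaluation comes before the first aquatic treatment.

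**Working it through.** **1. The plan's own figure.** The minimum of 102 is given for a medium effect, power 0.8 and significance level 0.05. The protocol gives no number for medium and does not say whether the test is one- or two-sided. Assume a standardised difference d = 0.5.

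- One-sided, normal approximation: 2 × (1.645 + 0.842)² / 0.5² ≈ 49.5, so 50 per arm and 100 in all. The t-test gives 50.15, so 51 per arm and 102 in all, an exact match.
- Two-sided t-test: 63.77, so 64 per arm and 128 in all.
- Two-sided ANCOVA with baseline correlation 0.45: power is 0.7995 at 102, and 104 are needed for 0.80.

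The figure can thus be reached without any covariate. It does not show that each endpoint must have its own baseline.

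**2. What ANCOVA needs.** The model is Y = a + t × arm + b × X + error. The comparison of arms, t, is valid in a randomised trial whenever X is fixed before treatment can affect it. X need not be an earlier measurement of Y. If X is left out, t is the difference in means, which is also valid. A covariate related to Y improves precision.

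**3. Which covariates exist.**

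| Endpoint in section 5.0 | When measured | Covariate available |
|---|---|---|
| Sit to stand | Initial evaluation; re-evaluation or discharge | Its own initial value |
| GRoC | Re-evaluation or discharge only | Initial sit to stand, initial pain, age |
| Borg | End of each session | Session 1, before the metronome starts |

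An ANCOVA of GRoC on initial sit to stand or pain satisfies the wording of section 5.0. Borg is in a similar position, since no covariate is named for it either.

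**4. What the missing GRoC baseline costs.** It costs precision only. For a two-sided F test with f = d/2 = 0.25, the noncentrality is N × f² / (1 − r²), where r is the correlation of covariate and outcome. At N = 102:

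- no covariate: 102 × 0.0625 = 6.375, power 0.71
- r = 0.3: 6.375 / 0.91 = 7.01, power 0.75
- r = 0.5: 6.375 / 0.75 = 8.50, power 0.82

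Without a covariate, one-sided power is 0.81 at 102 and 0.86 at 120; two-sided power at 120 is 0.78. These r values are assumptions.

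**5. What a search among models would do.** The simulation used 20,000 runs per cell, no true effect, equal arms and a two-sided 5% test. The smallest p-value was kept from four linear models for GRoC: no covariate, sit to stand, pain, or both. The correlation of GRoC with each covariate was assumed to be 0.1, 0.3 or 0.5, and the correlation between covariates 0.2.

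| N | Smallest p of four models | One fixed model, both covariates |
|---|---|---|
| 102 | 0.062, 0.082, 0.103 | 0.051, 0.052, 0.049 |
| 120 | 0.062, 0.075, 0.103 | 0.051, 0.048, 0.050 |

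The inflation comes entirely from the search. It would arise in any trial where the covariate set was picked this way, and it does not measure a fault in this protocol.

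**6. The consent sentence.** Section 2.0 places the scores in the patient's electronic chart, names the initial evaluation as a data source, and lists pain and sit to stand among the elements to be abstracted. Recruitment begins at the initial evaluation and consent follows at the first aquatic session. Read together, these say that the evaluation is routine care, its results are charted, and study abstraction follows consent. On that reading the initial values are available for the ANCOVA.

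**The case for a change.** The strongest case for a change is that this is more than an omission. The protocol does fix the analysis, in one sentence meant for every endpoint, and most readers would take baseline data to mean the earlier value of the outcome. That reading fits sit to stand and cannot fit GRoC, so an analysis plan would have to interpret the sentence before using it. Pairing GRoC with sit to stand under an improvement in scores points the same way. Naming the covariate would cost a sentence or two and no new data.

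Part of this stands. The covariate for GRoC is not named, nor is the one for Borg, and naming both in advance would be tidier. But the stricter reading is supplied by the reader. The sentence itself does not tie the covariate to the outcome, and an analysis on another initial measure complies with it. The improvement wording is equally weak as evidence, because GRoC is a rating of progress and a favourable score already records improvement. Allocating covariates to endpoints is commonly left to the analysis plan, which may exist but is not at hand. On consent, the literal clash is real as wording, but the data flow in section 2.0 resolves it.

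**Conclusion.** No change is needed. GRoC has no baseline of its own, but the stated method does not need one. Covariates measured before the metronome is used are already collected, and an unadjusted comparison is valid too. What remains is an unnamed covariate, a gap that analysts fill sensibly. Its cost is some precision on one of three endpoint measures: under the assumed medium effect of 0.5 and a two-sided test at 102 participants, power is 0.71 without a covariate against 0.75 to 0.82 with one correlated at 0.3 to 0.5. The 0.06 to 0.10 error range should carry no weight, because it presupposes a search for the smallest p-value that the protocol does not suggest.

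This conclusion rests on three assumptions: that the model for GRoC is chosen without sight of results by arm, that initial-evaluation values are abstracted from the chart after consent, and that baseline data is read as its plain words allow. If the analysis plan showed the GRoC model being picked after unblinded results, the matter would need to be reopened.
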